Patients will be assessed for disease response at the completion of 4 cycles of treatment. If there has been no response to therapy (i.e. stable disease per IWG-2006), or if disease progression is identified, patients will be eligible to continue on the study with the addition of 5-azacitadine or decitabine, with continuation of Pacritinib, in **Part 2** (Pacritinib + HMA). Patients responding to therapy will continue on Pacritinib monotherapy. Patients with disease progression prior to 4 cycles of Pacritinib are also eligible to initiate the Pacritinib + HMA study portion prior to the completion of 4 cycles. In these patients, disease assessment including bone marrow aspiration should be performed prior to the initiation of Part 2. Patients receiving Pacritinib + HMA will be re-assessed for disease response after 4 cycles of *combination* treatment on Part 2. Patients on pacritinib monotherapy in Part 1 who manifest disease progression at any time, including before or after completion of 4 cycles of treatment, can continue on study in Part 2 with the addition of a hypomethylating agent.

The addition of HMA should be initiated on Day 1 of the next Pacritinib treatment cycle whenever possible. HMA dosing and dosing adjustments should be performed according to the approved package insert, or at a dose of decitabine 20mg/m² IV over 1 hour for 5 days every 4 weeks and according to standard of care (see Section 5.0 for rules of dose reduction or delay).

Duration of Therapy

All patients must complete a screening visit, day 1 visits for each new cycle (+/- 5 days), end of treatment visit and whenever possible, an end of study safety visit 28 days after the last dose of Pacritinib (+/- 7 days).

Patients may remain on study for up to 12 months if the patient demonstrates clinical benefit and no excessive toxicity (i.e. no clinically significant study-drug related grade ≥ 3 toxicity). Patients who are experiencing clinical benefit beyond 12 months and have not experienced excessive toxicity may be eligible to continue therapy after discussion with the PI and the discussion documented in the patient's medical record. After the end of therapy and/or 30 days after your last dose of study drug, the study staff will follow your health status by phone call every 2 months (+/- 2 months) until you receive another cancer treatment.

Treatment is expected to continue until one of the following criteria applies:

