12.0 STATISTICAL CONSIDERATIONS

General Description

This is a Phase II open-label study designed to evaluate the efficacy and toxicity of Pacritinib as single agent (Part 1) and Pacritinib + HMA (Part 2) in subjects with lower-risk myelodysplastic syndrome. The primary efficacy outcome of both parts is the overall response rate (ORR) based mainly on hematologic improvement defined by IWG-2006 criteria, and which also includes complete remission (CR), partial remission (PR) and marrow complete remission. In Part 1, patient's overall response will be assessed after 1 cycle of treatment but no more than after 4 cycles of treatment; cycle length is 28 days. If no response is attained after 4 cycles of treatment or if progression occurs during therapy at any time, the patient is eligible to continue on Pacritinib + HMA (Part 2). Part 2 will not continue if Part 1 is stopped early. A maximum of 40 total evaluable patients (n=40) will be enrolled.

Study design: Part 1

The standard practice is to put these patients on observation, an ORR rate of about 15% is clinically relevant. The target ORR with the experimental treatment is 15%. The regimen of the Pacritinib will be considered worthy of further investigation if it elicits an increase in ORR to 15% with acceptable toxicity. A >15% therapy related non-hematological grade 3/4 toxicity rate is considered unacceptable. Thus, interim monitoring rules, assuming the prior distributions below, were constructed that meet the following two conditions,

- 1) Stop if $\text{Prob}\{p(\text{ORR}, E) < 0.15 \mid \text{data}\} > 0.975$, or
- 2) Stop if $\text{Prob}\{p(\text{TOX}, E) > 0.15 \mid \text{data}\} > 0.975$,

where $P(\text{ORR}, E)$ and $P(\text{TOX}, E)$ are the true ORR and toxicity rates for the Pacritinib, and $p(\text{ORR}, H)$ is the true ORR rate of the standard treatment. The first rule provides for stopping the study if the data suggest that it is unlikely (i.e., probability < 2.5%) that ORR rate of the Pacritinib treatment is greater than 15.0%. The second condition will stop the study early if excessive therapy-related non-hematological grade 3/4 toxicity (>15%) is highly probable (i.e., probability >97.5%) for the Pacritinib. Monitoring for toxicity and futility will not begin until 5 patients have been evaluated, and cohort size for future evaluations is 5.

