	0.20	0.2623
	0.25	0.2292
	0.30	0.2141
0.30	0.05	0.8956
	0.10	0.7815
	0.15	0.7182
	0.20	0.6879
	0.25	0.6378
	0.30	0.6675
0.40	0.05	0.9826
	0.10	0.9635
	0.15	0.9529
	0.20	0.9478
	0.25	0.9455
	0.30	0.9444
0.50	0.05	0.9990
	0.10	0.9979
	0.15	0.9973
	0.20	0.9970
	0.25	0.9969
	0.30	0.9968

Study design: Part 2

The standard practice is to put these patients on observation, an ORR rate of about 30% is

clinically relevant. The target ORR with the experimental treatment is 30%. The regimen of the Pacritinib + HMA will be considered worthy of further investigation if it elicits an increase in ORR to 30% with acceptable toxicity. A >30% therapy related non-hematological grade 3/4 toxicity rate is considered unacceptable. Thus, interim monitoring rules, assuming the prior distributions below, were constructed that meet the following two conditions,

- 1) Stop if $\text{Prob}\{p(\text{ORR}, E) < 0.30 \mid \text{data}\} > 0.975$, or
- 2) Stop if $\text{Prob}\{p(\text{TOX}, E) > 0.30 \mid \text{data}\} > 0.95$,

where $P(\text{ORR}, E)$ and $P(\text{TOX}, E)$ are the true ORR and toxicity rates for the Pacritinib + HMA, and $p(\text{ORR}, H)$ is the true ORR rate of the standard treatment. The first rule provides for stopping the study if the data suggest that it is unlikely (i.e., probability < 2.5%) that ORR rate of the Pacritinib + HMA treatment is greater than 30.0%. The second condition will stop the study early if excessive therapy-related non-hematological grade 3/4 toxicity (>30.0%) is highly probable (i.e., probability >95.0%) for the Pacritinib + HMA. Monitoring for toxicity and futility will not begin until 5 patients have been evaluated, and cohort size for future evaluations is 5. The monitoring rule for the toxicity rate, based on these assumptions and monitoring conditions above is found in Table 14. For example, accrual will cease if 4 or more patients experience toxicities among the first 5 patients.

Table 14. Stop accrual if the number of drug-related non-hematological grade 3/4 toxicities is greater than or equal to indicated (i.e., # patients with toxicities) among the number of patients evaluated								
# patients evaluated	5	10	15	20	25	30	35	40
# patients with toxicities	4-5	6-10	8-15	10-20	12-25	14-30	16-35	Always stop with this many patients

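### Table 16 leaves out the Part 1 stop and the limited supply of Part 2 patients, so it is not the probability that Part 2 ends early; what a crossed Part 2 boundary closes is also ambiguous

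*Combined protocol and SAP*

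**What the plan says.** Section 12.0, General Description, sets one enrolment figure for the whole study: "A maximum of 40 total evaluable patients (n=40) will be enrolled". It ties the parts together: "Part 2 will not continue if Part 1 is stopped early". That sentence does not distinguish a futility stop from a toxicity stop.

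Part 2 has no recruitment of its own. Patients reach it from Part 1, either without a response after four cycles or on progression. Section 4.0, Agent Administration, adds that monotherapy patients "who manifest disease progression at any time, including before or after completion of 4 cycles of treatment, can continue on study in Part 2". Section 4.0, Duration of Therapy, and section 11.0 repeat the eligibility. None of these places mentions a crossed Part 2 boundary.

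Under Study design: Part 2, the action is worded in two ways. Table 14 reads "Stop accrual if the number of drug-related non-hematological grade 3/4 toxicities is greater than or equal to indicated", and its example is "For example, accrual will cease if 4 or more patients experience toxicities among the first 5 patients". Table 15 likewise stops accrual. The rule text says instead: "The second condition will stop the study early if excessive therapy-related non-hematological grade 3/4 toxicity (>30.0%) is highly probable".

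Table 16 then lists probabilities of stopping the trial early for 25 combinations of true toxicity rate and true ORR. The accompanying text names the Part 2 priors and reference rates. It mentions neither Part 1 nor the number of patients expected to enter Part 2.

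**The concern.** Table 16 is what a reader would use to judge how often Part 2 would be cut short. Two features of the written design bear on that and are not visible in the table.

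First, any early stop of Part 1 ends Part 2, so a good combination can be closed because monotherapy was inactive. Second, the rules are run as if 40 patients will enter Part 2, while the only source is whichever of 40 Part 1 patients fail to respond or progress. The later looks may never be reached, which weakens protection against a toxic combination.

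The two omissions act in opposite directions, so the table cannot be read as conservative or as optimistic throughout.

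Separately, the Part 2 toxicity rule exists to limit exposure to the combination. It can do so only if the plan says what closes when the boundary is crossed.

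**Working it through.** **Inputs (section 12.0).** Part 1: Beta(0.3, 1.7) priors, reference rate 0.15, cutoffs 0.975 for futility and toxicity. Part 2: Beta(0.6, 1.4) priors, reference rate 0.30, cutoffs 0.975 for futility and 0.95 for toxicity. Looks at 5, 10, ..., 35 patients in each part.

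**Step 1: boundaries.** Stop when the Beta posterior tail probability exceeds the cutoff. This reproduces Tables 11, 12, 14 and 15 exactly.

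**Step 2: Table 16.** With response and toxicity independent, P(stop) = 1 − P(no futility crossing) × P(no toxicity crossing), each factor from an exact binomial recursion over the looks.

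| Part 2 toxicity / ORR | No futility crossing | No toxicity crossing | P(stop) | Printed |
|---|---|---|---|---|
| 20% / 30% | 0.9157 | 0.9851 | 0.0979 | 0.0979 |
| 10% / 50% | 0.9986 | 0.9994 | 0.0020 | 0.0020 |
| 30% / 30% | 0.9157 | 0.8769 | 0.1970 | 0.1970 |
| 50% / 30% | 0.9157 | 0.1655 | 0.848 | 0.8484 |

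All 25 cells reproduce this way, so the table contains no Part 1 term. (The prose gives 14.3% for the 30%/30% cell. That is a separate inconsistency; the table value is used here.)

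**Step 3: probability that Part 1 stops early.** Same method, Tables 11 and 12, looks every five patients:

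| Part 1 toxicity / ORR | No futility crossing | No toxicity crossing | P(Part 1 stops) | Futility alone |
|---|---|---|---|---|
| 15% / 15% | 0.8924 | 0.9557 | 0.147 | 0.108 |
| 10% / 10% | 0.7235 | 0.9944 | 0.281 | 0.277 |
| 10% / 5% | 0.3673 | 0.9944 | 0.635 | 0.633 |

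Table 13 prints 0.2194 at 15/15. The Table 13 cells checked reproduce with looks every four patients rather than the stated five, so the five-patient figures are used.

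**Step 4: add the Part 1 trigger.** With independent parts, P(Part 2 ends early) = 1 − (1 − P1)(1 − P2).

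- 20%/30% cell: 1 − 0.853 × 0.9021 = 0.23; 1 − 0.719 × 0.9021 = 0.35; 1 − 0.365 × 0.9021 = 0.67.
- 10%/50% cell: 1 − 0.853 × 0.998 = 0.15; 1 − 0.719 × 0.998 = 0.28; 1 − 0.365 × 0.998 = 0.64.

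**Step 5: add the limited feed.** At a Part 1 ORR of 15%, 40 × 0.85 = 34 non-responders are expected. The chance of at least 35, enough for the last look, is 0.43. At an ORR of 30%, 28 are expected and that chance is 0.009. Later progression of responders would add some entrants and is not counted.

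With Part 1 at 15/15, apply Tables 14 and 15 only to the entrants available and end Part 2 if Part 1 stops. For the 50%/30% cell (printed 0.848):

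| Share of non-responders entering (assumed) | Own crossing, given Part 1 completes | Joint: 0.147 + 0.853 × own crossing |
|---|---|---|
| 100% | 0.822 | 0.85 |
| 75% | 0.730 | 0.77 |
| 50% | 0.564 | 0.63 |

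In the 30%/30% cell (printed 0.1970) the joint figure is 0.31 with full entry and 0.25 with half. In the 10%/50% cell it stays at about 0.15 either way.

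**Step 6: the action.** Three readings fit the text: enrolment into Part 1 closes, entry into Part 2 closes, or the whole study stops. On the first, roll-over continues after a combination-toxicity signal. Sections 4.0 and 11.0 do not resolve this.

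**The case against.** The link between the parts is an explicit design statement, and Table 13 already gives a Part 1 stopping probability, so a reader could combine the tables. That is fair as far as it goes: the link is a choice, not an error. But nothing tells the reader to combine them, Table 13 does not match the stated look schedule, and no table carries the limited feed.

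Several stronger readings are tempting and are not supported.

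- A reader might infer that the Part 2 toxicity rule is void because Part 2 has no accrual. Part 2 does have an intake by roll-over, and Tables 14 and 15 sit under its own heading, so accrual can naturally mean entry to Part 2. The rule text also speaks of stopping the study, which would not leave roll-over open. General eligibility wording in sections 4.0 and 11.0 does not override a stopping rule. The defect is ambiguity.
- A reader might argue that all 40 patients would already be enrolled when a Part 2 signal appears. No accrual rate is stated, and the argument borrows the four-cycle response window. The toxicity rule states no such window, so toxicity looks may come much earlier.
- A reader might infer that Table 16 is too low throughout. With Part 1 at 15/15, the 50%/30% cell is about right with full entry and too high with partial entry.
- Relabelling Table 16 as conditional on Part 1 completing would also be wrong. For that cell the conditional figure is 0.82, 0.73 or 0.56 at 100%, 75% or 50% entry, not 0.848.
- Using Table 13's printed values in step 4 would give 30%, 42% and 72% for the 20%/30% cell, but those inputs do not belong to five-patient looks.

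**Conclusion.** The point holds in two parts. Table 16 does not give the probability that Part 2 ends early under the design as written. It understates that probability where Part 2's own stopping risk is low, with the 0.2% cell becoming about 15% to 64% and the 9.8% cell about 23% to 67% across the Part 1 scenarios. With Part 1 at 15/15 and partial roll-over, it overstates the chance of stopping a toxic combination. The size depends on assumptions the documents do not fix: the true Part 1 rates, the share of non-responders who enter, and independence between the parts and between response and toxicity.

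The action at a Part 2 boundary is ambiguous, and on a literal enrolment reading the toxicity rule would not limit combination exposure. The boundaries themselves are not in question; they follow from the stated priors and cutoffs.

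**What to change.** Recompute Table 16 jointly with the Part 1 stop and the Part 2 feed, using the stated look schedule and giving the assumed Part 1 rates and entry share, with a range for each. If the present figures are kept, label them as Part 2 boundaries alone with 40 Part 2 patients.

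Reconcile section 12.0 (General Description, the Part 2 rule text, Tables 14 and 15) with sections 4.0 and 11.0. The rule should state whether crossing a Part 2 boundary closes entry to Part 2, enrolment to Part 1, or both. It should also state whether the sentence ending Part 2 on an early Part 1 stop covers a futility stop. The roll-over text should then cross-refer to it. Which action is right is for the investigators to decide.

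The cost is wording and one recomputed table. The stated stopping figures become less favourable in the low-risk cells.

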Monitoring the ORR rate, based on the above assumptions and monitoring conditions is found in Table 15. For example, accrual will cease if 0 patients experience an overall response within 4 cycles in the first 10 patients treated.

Table 15. Stop accrual if the number with overall response is less than or equal to indicated (i.e., # patients with overall response) among the number of patients evaluated								
# patients evaluated	5	10	15	20	25	30	35	40
# patients with	Never stop	0	0-1	0-2	0-3	0-4	0-5	Always stop

overall response	with this many patients							with this many patients
------------------	-------------------------------	--	--	--	--	--	--	-------------------------------

Multic Lean Desktop (version 2.1.0) was used to generate the toxicity and futility stopping boundaries and the OC table (Table 16). In order to utilize the software for the design, a response constant rate of 0.30 and beta (0.6, 1.4) priors were assumed for the standard treatment response distribution and experimental treatment response prior distribution, respectively. In addition, a 30% toxicity constant rate and beta (0.6, 1.4) priors were assumed for the standard treatment toxicity constant rate and experimental treatment toxicity prior distribution, respectively.

The probability of stopping the study early if the true ORR of the Pacritinib + HMA was 30% and the true toxicity rate was 30% was 14.3%. Probabilities of stopping early for high true toxicity rates (i.e., 50%) were 84.4% when the true ORR was 30%, and 83.6% when true ORR rate was 40%.

Table 16 Operating characteristics for simultaneous monitoring response and toxicity rates for patients treated with Pacritinib treatment		
True Toxicity Rate	True ORR	Prob(stop the trial early)
0.10	0.10	0.9090
	0.20	0.3994
	0.30	0.0848
	0.40	0.0127
	0.50	0.0020
0.20	0.10	0.9103
	0.20	0.4079
	0.30	0.0979
	0.40	0.0268
	0.50	0.0163
0.30	0.10	0.9202
	0.20	0.4730
	0.30	0.1970
	0.40	0.1337
	0.50	0.1243
0.40	0.10	0.9505
	0.20	0.6734
	0.30	0.5023
	0.40	0.4631

	0.50	0.4573
0.50	0.10	0.9849
	0.20	0.9005
	0.30	0.8484
	0.40	0.8365
	0.50	0.8347

Statistical Analysis Plan

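### Part 2 text gives a 14.3% chance of stopping early at 30% response and 30% toxicity; Table 16 and the stated rule both give 19.7%

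*Combined protocol and SAP*

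**What the plan says.** All of this is in Section 12.0 Statistical Considerations, under Study design: Part 2.

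- **The rule.** Futility stops accrual when it is unlikely ("i.e., probability < 2.5%) that ORR rate of the Pacritinib + HMA treatment is greater than 30.0" per cent). Toxicity stops it when a rate above 30% is "highly probable (i.e., probability >95.0%) for the Pacritinib + HMA". Both rates have Beta(0.6, 1.4) priors and a fixed reference of 0.30.
- **The looks.** "Monitoring for toxicity and futility will not begin until 5 patients have been evaluated, and cohort size for future evaluations is 5".
- **The text on operating characteristics.** The probability of stopping early "if the true ORR of the Pacritinib + HMA was 30% and the true toxicity rate was 30% was 14.3" per cent. For high true toxicity the next sentence reads: "i.e., 50%) were 84.4% when the true ORR was 30%, and 83.6% when true ORR rate was 40" per cent.
- **Table 16.** The same three scenarios are printed as 0.1970 (toxicity 0.30, ORR 0.30), 0.8484 (toxicity 0.50, ORR 0.30) and 0.8365 (toxicity 0.50, ORR 0.40).

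**The concern.** The sentences introduce Table 16 and should agree with it. In Part 1 the corresponding text (21.9%, 95.3%, 94.4%) does match the entries of its own Table 13 (0.2194, 0.9529, 0.9444). In Part 2, two of the three figures do not match: 14.3% against 0.1970, and 84.4% against 0.8484. The first gap is far too large to be rounding.

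The 30%/30% scenario is the design's own reference point. The target ORR is 30%, and only toxicity above 30% is called unacceptable. This is therefore the chance of halting a combination that just meets both requirements. It is the first Part 2 operating characteristic the text quotes. If the sentence were right and the table wrong, the boundaries in Tables 14 and 15 would also be in doubt, so it matters which of the two is in error.

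**Working it through.** **Inputs (Section 12.0, Part 2).** Beta(0.6, 1.4) priors for response and toxicity; reference rate 0.30 for each; cutoffs 0.975 (futility) and 0.95 (toxicity); looks at 5, 10, …, 35 patients. Forty patients is the end of the trial, so a stop there is not early. Response and toxicity are taken as independent.

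**Step 1: boundaries.** With x events in n patients the posterior is Beta(0.6 + x, 1.4 + n − x). Stop for toxicity if Pr(rate > 0.30) > 0.95, and for futility if Pr(rate < 0.30) > 0.975. At n = 10:

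- 6 toxicities: Beta(6.6, 5.4), probability 0.962, stop. 5 toxicities: Beta(5.6, 6.4), 0.880, continue.
- 0 responses: Beta(0.6, 11.4), probability 0.993, stop. 1 response: Beta(1.6, 10.4), 0.937, continue.

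Over all looks:

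| n | 5 | 10 | 15 | 20 | 25 | 30 | 35 |
|---|---|---|---|---|---|---|---|
| Stop if toxicities ≥ | 4 | 6 | 8 | 10 | 12 | 14 | 16 |
| Stop if responses ≤ | none | 0 | 1 | 2 | 3 | 4 | 5 |

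These are exactly Tables 14 and 15.

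**Step 2: probability of an early stop.** For each endpoint, the binomial distribution of the count is carried from look to look and the stopped paths are removed. With F the futility stop and T the toxicity stop,

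P(stop early) = 1 − (1 − F)(1 − T).

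| True toxicity / ORR | F | T | P(stop early) | Table 16 | Text |
|---|---|---|---|---|---|
| 30% / 30% | 0.0843 | 0.1231 | 1 − 0.9157 × 0.8769 = 0.1970 | 0.1970 | 14.3% |
| 50% / 30% | 0.0843 | 0.8345 | 1 − 0.9157 × 0.1655 = 0.8484 | 0.8484 | 84.4% |
| 50% / 40% | 0.0121 | 0.8345 | 1 − 0.9879 × 0.1655 = 0.8365 | 0.8365 | 83.6% |

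The same calculation reproduces all 25 cells of Table 16, with a largest deviation of 0.00005. Rule, boundaries and table form one consistent set, and the text is the outlier.

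**Step 3: can another reading rescue 14.3%?**

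- Adding a look at 40 gives 0.2042. Dropping the look at 5 gives 0.186, and dropping the look at 35 gives 0.187.
- With the stated futility cutoff, 14.3% arises only for a toxicity cutoff of 0.970 to 0.975 (0.1428). The toxicity boundary is then 4/5, 7/10, 9/15, 11/20, 13/25, 15/30, 17/35, which is not Table 14. The two figures in the next sentence would become 74.4% and 72.4%.
- Varying both cutoffs from 0.900 to 0.995 in steps of 0.001, with the same priors and looks, gives 221 distinct boundary pairs. None yields 14.3%, 84.4% and 83.6% together; the best matches two.

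**Step 4: does the size of Part 2 matter?** The plan states "A maximum of 40 total evaluable patients (n=40) will be enrolled" but gives no number for Part 2. Any Part 2 size from 36 to 40 uses the same early looks, so Table 16 is unchanged. With 34 patients (looks 5 to 30) the figures are 18.7% at 30%/30%, 81.0% at toxicity 50% / ORR 30%, and 87.0% at 10%/10%. The text would still be 18.7 − 14.3 = 4.4 points too low.

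**The case against.** The best defence is that little depends on the sentence. The right value is printed directly below it under the same labels, the boundaries that will be applied follow the stated rule, and no stopping decision, sample size or analysis uses the text figure. That stands, and it limits the harm. It does not make the sentence correct, and a reader who takes the summary at face value gets the wrong figure for the key scenario.

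Other points are fair in part:

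- The 84.4% slip is only 0.4 points and is secondary.
- The exact third value is 0.83651, so 83.6% is a truncation rather than a rounding. It is immaterial.
- Calling a stop at 30%/30% wrong is somewhat strong, because toxicity is then exactly on the limit. The neutral description is the chance of stopping at the target ORR and the toxicity limit.
- The search over cutoffs covers only these priors, looks and ranges. It shows that the three figures do not come from one such rule, but not where 14.3% came from. A leftover from a version with a 0.975 toxicity cutoff is possible and unproven.
- The 34-patient figures rest on an assumption and concern a side question. The contradiction between text and table does not need them.

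**Conclusion.** The concern holds. For the Part 2 rule as written, the probability of stopping early at 30% ORR and 30% toxicity is 19.7%, not 14.3%. The text understates it by 19.7 − 14.3 = 5.4 percentage points. The 84.4% should be 84.8%, a 0.4-point slip that slightly undersells the design. The 83.6% agrees with Table 16 to within 0.1 point.

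The result assumes independent response and toxicity, looks every 5 patients, and at least 36 patients in Part 2. The exact match with all of Table 16 indicates that its authors' calculation did the same. This is a demonstrable error in a headline design property and should be corrected. It does not affect the stopping boundaries or the conduct of the trial.

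**What to change.** First confirm that 0.95 is the intended Part 2 toxicity cutoff, as the stated rule and Tables 14 and 16 imply. Then bring the paragraph before Table 16 into line with the table: change 14.3% to 19.7% and 84.4% to 84.8%, and leave 83.6%. The cost is two percentages in one paragraph.

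Optionally, add a note that Table 16 assumes at least 36 patients enter Part 2, with one set of figures for a smaller number such as 34. At Part 1's 15% ORR, 40 × 0.85 = 34 non-responders are expected, and the binomial chance of 36 or more is 0.26. That count leaves out drop-outs and responders who progress later, although entry is also open to "Patients on pacritinib monotherapy in Part 1 who manifest disease progression at any time". The documents give no crossover or drop-out rate, so 34 is an assumption. This addition needs one rerun of the same software.

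### Table 16's Part 2 early-stopping probabilities need at least 35 Part 2 entrants, but Part 2 draws only on non-responders and progressors among at most 40 enrolled

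*Combined protocol and SAP*

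**What the plan says.** All references are to the combined protocol and SAP.

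- **Total size (12.0, General Description).** "A maximum of 40 total evaluable patients (n=40) will be enrolled". Section 4.0 gives the same cap.
- **Who enters Part 2 (12.0, General Description).** "If no response is attained after 4 cycles of treatment or if progression occurs during therapy at any time, the patient is eligible to continue", meaning entry to the combination. Entry is an option for the patient, not a requirement.
- **Responders (4.0).** "Patients responding to therapy will continue on Pacritinib monotherapy". Later entry is open to "Patients on pacritinib monotherapy in Part 1 who manifest disease progression at any time, including before or after completion of 4 cycles of treatment".
- **Link between the parts (12.0, General Description).** "Part 2 will not continue if Part 1 is stopped early".
- **Part 1 target (12.0, Study design: Part 1).** "The target ORR with the experimental treatment is 15" (per cent).
- **Part 2 rules (12.0, Study design: Part 2).** Looks begin at 5 patients and recur every 5. Tables 14 and 15 give stopping bounds at 5, 10, ..., 35; the column for 40 ends the part whatever the count. Table 16 gives the probability of stopping early, and the text before it says: "Probabilities of stopping early for high true toxicity rates (i.e., 50%) were 84.4% when the true ORR was 30" (per cent).

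The plan states no expected Part 2 size and gives no operating characteristics for fewer than 40 Part 2 patients.

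**The concern.** Tables 14 to 16 treat Part 2 as a cohort that can fill to 40. The trial enrols at most 40 in total, and a patient reaches Part 2 only after failing to respond in Part 1 or progressing there. Some patients will respond. Others may leave for transplant, toxicity, intercurrent illness or by request (4.0 and 11.0), or may decline the combination. The later looks may therefore never happen, and the probability mass that Table 16 credits to them is not available.

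The documents report no clinical data on pacritinib plus a hypomethylating agent. Table 16 is thus the plan's only quantified statement of how likely an unsafe or inactive combination is to be stopped. A reader should know what Part 2 size that statement presupposes.

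**Working it through.** **Inputs (12.0, Study design: Part 2).** Beta(0.6, 1.4) priors for response and for toxicity; comparison rate 0.30 for both; toxicity cut 0.95; futility cut 0.975; looks every 5 patients from 5.

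**Step 1: bounds.** With x events in n patients the posterior is Beta(0.6 + x, 1.4 + n − x). The toxicity bound is the smallest x with Pr(rate > 0.30) > 0.95. The futility bound is the largest x with Pr(rate < 0.30) > 0.975.

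- Toxicity at n = 5, 10, ..., 35: 4, 6, 8, 10, 12, 14, 16. This equals Table 14.
- Futility: none at 5, then 0, 1, 2, 3, 4, 5. This equals Table 15.

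**Step 2: reproduce Table 16.** An exact binomial recursion over the looks, with response and toxicity independent, uses

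P(stop) = 1 − P(no toxicity stop) × P(no futility stop).

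At toxicity 0.50 and ORR 0.30, with all looks through 35, this is 1 − 0.1655 × 0.9157 = 0.848, matching the table's 0.8484. All 25 cells match to four decimals. There is no early-stop look at 40, so the size that matters is 35 entrants.

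**Step 3: the same recursion, cut at the last look reached.**

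| True toxicity / ORR | 35 (as Table 16) | 30 | 25 | 20 |
|---|---|---|---|---|
| 0.50 / 0.30 | 0.848 | 0.810 | 0.757 | 0.685 |
| 0.40 / 0.30 | 0.502 | 0.469 | 0.429 | 0.377 |
| 0.20 / 0.10 (futility) | 0.910 | 0.872 | 0.813 | 0.724 |

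**Step 4: how many can enter.** At a 15% Part 1 ORR, 40 × 0.85 = 34 non-responders are expected, so the last look is at 30. Taking Part 2 size as Binomial(40, q) and averaging over the look that each size allows:

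| Share of non-responders who cross over (assumed) | q | Mean Part 2 size | P(at least 35) | P(stop) at 0.50 / 0.30 |
|---|---|---|---|---|
| 100% | 0.85 | 34.0 | 0.43 | 0.825 |
| 90% | 0.765 | 30.6 | 0.07 | 0.794 |
| 80% | 0.68 | 27.2 | 0.004 | 0.755 |
| 70% | 0.595 | 23.8 | about 0 | 0.707 |

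This table leaves out responders who progress later and then enter, so its chances of reaching 35 are biased low.

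**Step 5: allow late entry.** As an illustration, suppose half of the responders later progress and every eligible patient enters. Then q = 0.85 + 0.075 = 0.925, the mean size is 37, P(at least 35) = 0.92, and P(stop) = 0.8455, essentially the printed value.

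**Step 6: text against table.** For toxicity 30% and ORR 30% the text says 14.3% and Table 16 says 0.1970. The stated 0.95 toxicity cut gives 0.1970; a 0.975 cut gives 0.1428. For toxicity 50% and ORR 30% the text says 84.4%, whereas 0.8484 rounds to 84.8%.

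**The case against.** The strongest reply is that giving operating characteristics at the maximum size is ordinary practice, that the plan calls 40 a maximum, and that Table 16 is computed correctly. On the documents' own inputs the loss is small: 0.825 against 0.848 on average with full crossover. The larger drops need an uptake below 100%, and the plan gives no uptake figure. Late progressors may enter, and looks are triggered by patients evaluated rather than by calendar time, so a late entrant still counts toward a look. All of this stands, and it limits the size of the point.

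A reader might also infer that Part 2 patients are less protected against toxicity than the plan claims. The documents do not support that. The bounds at each look are unchanged, and so is the chance of having stopped by any given look. A smaller Part 2 loses only late looks, which would have spared patients who in that case never enter. At toxicity 0.50 and ORR 0.30 the expected number treated is 18.5 with a maximum of 40, 16.8 with 30 and 15.6 with 25.

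What remains is that the printed probability depends on a condition the plan does not state. At the plan's own target response rate, the expected number of non-responders (34) is one short of it.

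**Conclusion.** The point holds as one about reporting and design assumptions. Table 16 and the sentence before it are correct for a Part 2 of at least 35 entrants and are a ceiling for anything smaller.

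At toxicity 50% and ORR 30% the overstatement is about 2 points on average (0.848 − 0.825 = 0.023) at the 15% Part 1 target with full crossover, and about 4 points (0.848 − 0.810 = 0.038) if the last look is at 30. It would be 9 points (0.848 − 0.757 = 0.091) or 16 points (0.848 − 0.685 = 0.163) with a last look at 25 or 20, which rests on assumed non-crossover. It is near zero if most responders later progress and enter. A low Part 1 response rate also narrows the gap: at 10% the chance of at least 35 non-responders is 0.79. Part 1 is then more likely to stop early, however, and Part 2 would end with it.

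The direction is certain, because removing looks cannot raise the stopping probability. The size depends on uptake and late entry, which the documents do not give.

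**What to change.** 1. Leave the boundaries in Tables 14 and 15 as they are.
2. Recompute Table 16 by last look reached: 20, 25, 30 and 35.
3. State that the present figures are a ceiling that requires at least 35 Part 2 entrants.
4. In the text, give the figure for the Part 2 size expected at the 15% Part 1 ORR (34 non-responders, last look at 30: 0.810) beside the ceiling of 0.848. Quoting only a figure for a smaller Part 2 would bring in an uptake assumption that the plan does not make.
5. Reconcile the text with Table 16: 14.3% against 0.1970, and 84.4% against 0.8484. Confirm that both come from the toxicity cut-off stated in the rule.

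The cost is one re-run of the design software and an edit to one table and one paragraph. No patient number, boundary or decision rule changes. The downside is that the stated figures become slightly less favourable.
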